**Figure 1: Study Schema**

a. Screening from Day -28 to Day -1.

b. IS dosing schedule: 60 mg daily for the first 2 cycles (56 days) followed by 60 mg daily for 7 days of every 28-day cycle (7 days on / 21 days off treatment).

c. Follow-up Period will include: 1) EOT/30-Day Safety Follow-up visit will occur 30 ( $\pm 3$ ) days from the last day of study drug treatment. 2) Efficacy Follow-up - for subjects who discontinue study treatment due to reasons other than disease progression or death, response follow up will occur until PD or the start of a new anti-cancer therapy. 3) Survival Follow-up visits will occur every 3 months until death, and will continue for up to 3 years after the last subject is enrolled in the study.

d. Response assessments will be performed every 2 months ( $\pm 7$  days) for the first 6 months, every 3 months ( $\pm 7$  days) during the following 12 months, and every 6 months ( $\pm 14$  days) thereafter (starting with month 18).

Abbreviations: CS = continuous schedule; EOT = End of Treatment; FU = follow up; IS = intermittent schedule; PD = progressive disease.

For subjects who experience hematologic or non-hematologic adverse reactions, please refer to ME-401 toxicity management ([Table 4](#)) and modified dosing schedules in [Section 5.3.1](#).

ME-401 is provided as 60 mg capsules. ME-401 is to be taken orally once a day at approximately the same time each day in accordance with the IS regimen (or CS dosing regimen if switched from IS after PD).

Subjects must receive prophylaxis treatment for *Pneumocystis jirovecii* pneumonia (PJP) as prescribed within this protocol (see [Section 5.4.3](#)).

See the Schedule of Assessments ([Appendix 1](#)) for a detailed list of study procedures.

The Modified Lugano 2014 criteria will be used for response assessment ([Appendix 5](#)). The Investigator's assessment of disease response will be used for subject management. For the primary analysis, disease/response assessment will be performed by an IRRC blinded to Investigator assessment and treatment assignment. Methods for disease/response assessment by the IRRC are described in the IRRC Charter. Disease/response assessment will occur every 2 months for the first 6 months, every 3 months during the next 12 months, and every 6 months thereafter.

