Subjects will continue to receive study drug in accordance with the IS dosing regimen (or CS dosing regimen if switched from IS after PD) until Investigator-assessed disease progression or unmanageable toxicity requiring treatment discontinuation, subject's decision to withdraw their consent to participate on study, or study closure by the Sponsor. A notification to the Medical Monitor will be sent prior to subject discontinuation. The End of Treatment (EOT)/30-Day Safety Follow-up visit will occur 30 ( $\pm 3$ ) days from the last dose of study drug.

Subjects who discontinue study drug will remain in the study with follow-up conducted every 3 months from the last dose of study drug to obtain post-treatment long-term follow-up information on disease status (i.e., change in disease response, progression), start of subsequent therapy, and survival (death). During this post-treatment follow-up phase, all subjects discontinued for reasons other than PD must continue imaging tests to assess disease status, performed per the original protocol-defined schedule for disease/response assessment, or earlier if clinically indicated. Imaging test results will no longer be collected when a subject starts a new therapy or disease progression occurs. The progression will be documented in the post-treatment long-term follow-up phase. Survival follow-up will continue for up to 3 years after the last subject is enrolled in the study.

Plasma samples will be obtained from all subjects to evaluate ME-401 PK and to serve for ME-401 exposure-response and exposure-toxicity modeling. For subjects enrolled at US sites only, blood samples will be obtained for a correlative immune study. See Schedule of Assessments ([Appendix 1](#)) for blood sample collection.

The primary analysis of ORR for FL will occur after the initial 91 consecutive subjects randomized to or assigned to the IS arm, which represent the Primary Efficacy Population (PEP) (except those who discontinue early), have been followed for at least 6 months from the start of study drug. The final analysis of DOR for FL will occur after most responders in the PEP have at least 12 months of follow-up from first response.

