## **8.7. Post-Treatment Long-Term Follow-up**

All subjects who stop study drug treatment will be followed long-term by the site every 3 months from the last dose of study drug to obtain data regarding changes in efficacy assessments, death, or subsequent therapy based on SOC assessments, which includes tumor imaging tests based on the original protocol-defined schedule for response assessment. This will be captured on the post-treatment eCRF. All subjects will be followed for survival. Survival follow-up will continue for up to 3 years after the last subject is enrolled in the study. Follow-up will be discontinued if the subject withdraws consent to participate in the study.

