- z. **Opportunistic Infection Monitoring** – Prior to start of every cycle of treatment with ME-401, monitoring will be conducted, and for subjects with identified risk factors and those who developed an OI while on study treatment, additional assessments should include: CD4 and CD8 count and ratio, c-reactive protein, blood cultures, any additional laboratory and diagnostic methods according to local SOC reported as unscheduled laboratory and diagnostic methods of assessment, radiological imaging (i.e., chest X-ray or CT scans). Note: Treatment of the OI that started while on study should be based on local SOC.
- aa. **Post-treatment Follow-up Procedures** – Every 3 months from the last dose of study drug to obtain data regarding changes in efficacy assessments, death or subsequent therapy based on standard of care assessments. Imaging tests to assess disease status will be performed at least once every 6 months or earlier as indicated per standard of care. Any AE that has not returned to baseline or Grade  $\leq 2$  should be followed until it has returned to baseline or better, the event is assessed as stable by the Investigator, the subject is lost to follow up, or the subject withdraws consent. Survival follow-up will continue for up to 3 years after the last subject is enrolled in the study.
- bb. **Response assessment** – Imaging scans, physical examination, bone marrow aspirate/biopsy (if applicable), and laboratory evaluation as appropriate for individual subjects.
- cc. **Response assessment at the EOT/30-Day Safety Follow-up visit** – Perform imaging test (CT scan or PET/CT scan) only if last imaging tests outside the window noted for CT scan or PET-CT.
- dd. **CT Scan** – CT of the neck, chest, abdomen, and pelvis must be obtained at screening (within 6 weeks prior to Cycle 1 Day 1). CT scans must be performed using IV contrast. For subjects who are intolerant to contrast agents, the CT scan will be performed with oral contrast or MRI scans will be used.
- ee. **PET/CT** – FDG-PET scan must be obtained at screening (within 6 weeks prior to Cycle 1 Day 1), as indicated, and to confirm CR/CMR. PET/CT imaging is no longer needed once a CMR has been achieved and a CT scan is an appropriate imaging test.

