- z. **Opportunistic Infection Monitoring** – Prior to start of every cycle of treatment with ME-401, monitoring will be conducted, and for subjects with identified risk factors and those who developed an OI while on study treatment, additional assessments should include: CD4 and CD8 count and ratio, c-reactive protein, blood cultures, any additional laboratory and diagnostic methods according to local SOC reported as unscheduled laboratory and diagnostic methods of assessment, radiological imaging (i.e., chest X-ray or CT scans). Note: Treatment of the OI that started while on study should be based on local SOC.
- aa. **Post-treatment Follow-up Procedures** – Every 3 months from the last dose of study drug to obtain data regarding changes in efficacy assessments, death or subsequent therapy based on standard of care assessments. Imaging tests to assess disease status will be performed at least once every 6 months or earlier as indicated per standard of care. Any AE that has not returned to baseline or Grade  $\leq 2$  should be followed until it has returned to baseline or better, the event is assessed as stable by the Investigator, the subject is lost to follow up, or the subject withdraws consent. Survival follow-up will continue for up to 3 years after the last subject is enrolled in the study.
- bb. **Response assessment** – Imaging scans, physical examination, bone marrow aspirate/biopsy (if applicable), and laboratory evaluation as appropriate for individual subjects.
- cc. **Response assessment at the EOT/30-Day Safety Follow-up visit** – Perform imaging test (CT scan or PET/CT scan) only if last imaging tests outside the window noted for CT scan or PET-CT.
- dd. **CT Scan** – CT of the neck, chest, abdomen, and pelvis must be obtained at screening (within 6 weeks prior to Cycle 1 Day 1). CT scans must be performed using IV contrast. For subjects who are intolerant to contrast agents, the CT scan will be performed with oral contrast or MRI scans will be used.
- ee. **PET/CT** – FDG-PET scan must be obtained at screening (within 6 weeks prior to Cycle 1 Day 1), as indicated, and to confirm CR/CMR. PET/CT imaging is no longer needed once a CMR has been achieved and a CT scan is an appropriate imaging test.

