##### **3.2.2. Duration of Response (DOR) and Duration of Recaptured Response (DORR)**

DOR is defined as time from first (CR or PR) response to the time of first PD (based on the Modified Lugano Response Criteria) or the date of death due to any cause (whichever occurs earlier).

For Primary Analysis and NDA Analysis for FL, DOR will be analyzed based on the patients who achieved PR or CR prior to first PD, that is reported before the data cutoff date for the FL Primary Analysis.

As a supportive analysis for NDA Analysis for FL, DOR will be analyzed based on all patients who achieved PR or CR prior to first PD, that is reported before the data cutoff date for the NDA Analysis for FL submission.

To evaluate the duration of response for subjects who had recapture of response on the CS dosing ([Section 3.2.6](#)), DORR is defined as the time from recapture of response (CR or PR) to the time of second PD or the date of death due to any cause (whichever occurs earlier).

Detailed censoring rules are specified in [Table 2](#) (FDA guidance [[FDA 2015](#)] and [[FDA 2018](#)]). In general, in primary analysis for DOR and analysis for DORR, subjects will be censored at the date of last adequate assessment with evidence of no progression by the IRRC, in the following situations:

- No progression nor death
- Discontinuation for any reason other than IRRC documented PD or death, including loss to follow-up, toxicity, withdrawal of consent, etc.
- Start of new anti-lymphoma treatment without evidence of IRRC documented PD
- Death or progression after two or more consecutive missed scheduled visits.

Supportive analysis for DOR will be conducted to evaluate the robustness of the primary analysis result for DOR, by considering all progressions and deaths as events per European Medicines Agency (EMA) guidance ([EMA 2013](#)), regardless of whether they occurred after initiating next anti-lymphoma treatment, after 2 or more consecutive missed scheduled assessments, or being reported as clinical (non-IRRC reviewed radiographic) progression ([Table 3](#)).

For subjects in IS dosing switching to the CS at PD, both DOR and DORR will be estimated.

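### Post-treatment imaging follows the original schedule in the body text but only a 6-month minimum in footnote aa, so the dating or censoring of progression before month 18 is not fixed

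*Protocol*

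**What the plan says.** Three places put subjects who stop for a reason other than progression on the original imaging schedule. Protocol section 5.1 makes it mandatory, with scans "performed per the original protocol-defined schedule for disease/response assessment, or earlier if clinically indicated". Protocol section 8.7 asks for "tumor imaging tests based on the original protocol-defined schedule for response assessment". SAP section 2.3 repeats the section 5.1 rule below the study schema. The original schedule itself is: "Disease/response assessment will occur every 2 months for the first 6 months, every 3 months during the next 12 months, and every 6 months thereafter". In months that is 2, 4, 6, 9, 12, 15, 18, then 24, 30 and so on.

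Footnote aa to Protocol Appendix 1 sets a different requirement for the same period: "Imaging tests to assess disease status will be performed at least once every 6 months or earlier as indicated per standard of care". Footnote aa to SAP Table 1 carries it too: "Imaging tests to assess disease status will be performed at least once every 6 months".

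The consequences depend on the censoring rules in SAP section 3.2.2. For primary DOR, "subjects will be censored at the date of last adequate assessment with evidence of no progression by the IRRC" in several situations, one of them being "Discontinuation for any reason other than IRRC documented PD or death, including loss to follow-up, toxicity, withdrawal of consent, etc". Another is progression or death that follows at least two scheduled visits missed in a row. SAP section 3.2.4 gives PFS the rules of the primary DOR analysis, but cites Table 3, which is the supportive table.

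**The concern.** Sites are likely to work from the schedule of assessments. A site that scans every 6 months after a toxicity stop complies with footnote aa and deviates from sections 5.1 and 8.7. Scan frequency would then depend on whether the subject is still on drug.

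This can affect the results in two ways. First, progression is dated at the scan that reveals it, so a longer gap gives a later date. Second, a gap that passes over two original-schedule scans may count as two missed visits, and the progression is then censored instead of counted. DOR is the subject of the NDA Analysis for FL (SAP section 1.2), with rates reported at 3, 6, 9 and 12 months (SAP section 7.2.2). Those milestones fall mostly in the period where the two imaging rules differ. In a single-arm study an upward shift favours the drug, because no comparator is dated in the same way.

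**Working it through.** The plan states no figure on this point, so there is none to reproduce. The schedule is consistent: months × 30.4375 days (the SAP's conversion) agrees with the Appendix 1 study days within 1 day, for example 9 × 30.4375 = 273.9 against Day 274.

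**1. Added detection delay.** Let the last scan be at month *a*, and let a footnote-only site scan next at *a* + 6. Progression falls at time *t*, uniform over that gap, and *s(t)* is the first original-schedule scan at or after *t*. The added delay is (*a* + 6) − *s(t)*. For *a* = 4 the next footnote scan is at month 10:
- progression in months 4–6 adds 10 − 6 = 4
- progression in months 6–9 adds 10 − 9 = 1
- progression in months 9–10 adds 10 − 12 = −2
- mean = (2×4 + 3×1 − 1×2)/6 = 1.5 months

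| Last scan (month) | Next footnote scan | Original scans skipped | Mean lag, original | Mean lag, footnote | Mean added | Max added |
|---|---|---|---|---|---|---|
| 0 | 6 | 2, 4 | 1.0 | 3.0 | 2.0 | 4 |
| 2 | 8 | 4, 6 | 1.33 | 3.0 | 1.67 | 4 |
| 4 | 10 | 6, 9 | 1.5 | 3.0 | 1.5 | 4 |
| 6 | 12 | 9 | 1.5 | 3.0 | 1.5 | 3 |
| 9 | 15 | 12 | 1.5 | 3.0 | 1.5 | 3 |
| 12 | 18 | 15 | 1.5 | 3.0 | 1.5 | 3 |
| 15 | 21 | 18 | 3.0 | 3.0 | 0 | 3 |
| 18 | 24 | none | 3.0 | 3.0 | 0 | 0 |

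The month 0 row matters for PFS only, since a responder has at least one post-baseline scan.

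**2. Missed-visit rule.** With a last scan at month 4 or earlier, the first footnote gap passes over two original scans. If the original schedule defines what is scheduled, the rule applies although nothing the footnote requires was missed. With a last scan at months 6 to 15, the first gap passes over one and the rule does not apply.

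**3. Size of the affected group.** In the Phase 1b IS group (Protocol section 1.6.2.3), 13 of 43 stopped: 9 for progression, 2 for AEs, 1 by withdrawing consent and 1 for transplant. AE stops are 2/43 = 4.7% at a median follow-up of 155 days. Crudely scaled to 18 months, 4.7% × 548/155 is about 16%. I assume 5% to 20% by month 18. For median DOR I take 11.2 months (Protocol section 1.6.2.4) and, as an assumption, 18 months, because section 2.3 reports the IS median as not reached at a later cut.

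**4. Effect on the DOR curve.** I simulated 200,000 responders per scenario, with exponential DOR, first response at month 2 and exponential time to toxicity stop. The Kaplan-Meier 12-month DOR rates (%) are:

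| Median DOR | Stops by month 18 | Original schedule | Footnote, every PD counted | Footnote, with missed-visit rule |
|---|---|---|---|---|
| 11.2 | 5% | 53.7 | 53.7 (0.0) | 54.1 (+0.4) |
| 11.2 | 10% | 53.8 | 53.9 (+0.1) | 54.7 (+0.9) |
| 11.2 | 20% | 53.9 | 53.9 (0.0) | 55.7 (+1.8) |
| 18 | 5% | 68.0 | 68.0 (0.0) | 68.4 (+0.4) |
| 18 | 10% | 68.1 | 68.1 (0.0) | 68.8 (+0.7) |
| 18 | 20% | 68.0 | 68.0 (0.0) | 69.5 (+1.5) |

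The Kaplan-Meier median stayed at 13 and 22 months on the scan grid in every scenario. The missed-visit rule censored 0.7% to 4.1% of responders. Late dating alone has no consistent sign: the 6-month rate moved by −0.3 to 0.0 points and the 9-month rate by 0.0 to +0.4. If all toxicity stoppers are censored at their last scan before stopping, later scans cannot enter and the schedules differ by 0. PFS was not simulated.

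**5. Scale.** With about 91 × 0.655 = 60 responders, the standard error of a 53.7% rate is √(0.537 × 0.463/60) = 6.4 points, ignoring censoring.

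**The case against.** The strongest reply is that the SAP already disposes of these progressions. Its discontinuation rule names toxicity and censors at the last adequate scan. Table 3 words its own row as treatment discontinuation and does not mark it as differing from the primary analysis, which suggests that Table 2 means the same. On that reading the imaging interval has no effect. The reading is possible but not settled. Table 2 also makes documented progression an event without limiting it to time on drug. Its row for new anti-lymphoma treatment would have little left to do. The protocol also mandates response follow-up after a stop until progression or new therapy, which would serve DOR and PFS little if every such progression were discarded.

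Second, the footnote is a minimum, so a site on the original schedule satisfies both texts. That stands, and how many sites would use the footnote alone is not in the documents. It does not remove the conflict, because the footnote permits what section 5.1 does not.

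Third, follow-up contacts remain 3-monthly, so a skipped scan need not be a missed visit. This is arguable. SAP section 3.2.2 states the rule once in terms of visits and once in terms of assessments.

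Fourth, late dating and missed-visit censoring cannot both apply to one progression. That is correct, and they are shown separately above.

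Fifth, enrollment is closed. Scans already taken cannot change, but an MZL subject who started near the closure date of 31 August 2022 reaches month 18 only around the end of February 2024.

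Finally, DOR and PFS are descriptive, and any shift is small against sampling error. That stands and limits the weight of the point.

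**Conclusion.** The contradiction is plain and sits in both documents. Before month 18 it leaves open when a progression after a toxicity stop is found and, together with the SAP's wording, whether it counts as an event. A footnote-only site can find it up to 3 to 4 months later, on average 1.5 to 2.0 months later if the last scan was by month 12. The possible bias on the 12-month DOR rate is upward and small, about 0 to 2 points. Nearly all of it comes through the missed-visit rule. It is zero under a literal reading of Table 2's discontinuation row. These sizes rest on assumed toxicity stops of 5% to 20% by month 18, assumed exponential DOR with medians of 11.2 or 18 months, and every affected site using the footnote minimum.

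A reader might infer that DOR and PFS are inflated as a matter of course, or that the median DOR is lengthened. The documents do not support that: the censoring rules may exclude these progressions altogether, and the median did not move in any of these scenarios. A reader might also assume that 20% to 40% of subjects a year stop without progression. At up to 40% a year, with medians of 9 to 12 months, the missed-visit route reaches about 3 points. The Phase 1b IS figure, however, is 2 of 43 stopping for AEs, roughly 4.7% × 365/155 = 11% a year. The primary ORR test and its sample size do not depend on this point.

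**What to change.** - **Footnote aa, Protocol Appendix 1 and SAP Table 1:** reconcile it with Protocol sections 5.1 and 8.7 and SAP section 2.3 by replacing the 6-month minimum with a reference to the original response-assessment schedule, until progression or new anti-cancer therapy.
- **SAP section 3.2.2 and Tables 2 and 3:** state whether IRRC-documented progression on a scan after treatment stops, before new therapy, is an event or is censored under the discontinuation row. State which schedule defines a missed scheduled visit, and use one term for visits or assessments.
- **SAP section 3.2.4:** reconcile the Table 3 citation for PFS with the stated intent to follow the primary DOR rules, which are in Table 2.

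The cost is one footnote edit in each document and a few clarifying sentences in the SAP. No scans are added beyond those the body text already requires.

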**APPENDIX 2. COCKCROFT-GAULT EQUATION FOR ESTIMATED CREATININE CLEARANCE**

Estimate the subject's creatinine clearance using the serum creatinine value provided by the local laboratory, actual body weight, and the appropriate Cockcroft-Gault formula (if necessary, convert serum creatinine values from  $\mu\text{mol/L}$  to  $\text{mg/dL}$  by dividing by 88.4; for example, 100  $\mu\text{mol/L}$  divided by 88.4 equals 1.131  $\text{mg/dL}$ ):

[figure not shown]
**Estimated Creatinine Clearance ( $C_{Cr}$ ) by the Cockcroft-Gault Equation:**

$$C_{Cr} = \frac{(140 - \text{age in years}) \times (\text{weight in kg})}{72 \times (\text{serum creatinine in mg/dL})} \times (0.85 \text{ if female})$$

Abbreviations:  $C_{Cr}$  = creatinine clearance (in mL/minute)

**APPENDIX 3. SKIN ASSESSMENT**

In the event of cutaneous or mucosal disease, the following assessments are required:				
Date Rash or Mucosal Disease Began	_____			
Date Resolved	_____			
Date of Consultation	_____			
Event date as related to the study Cycle 1 Day 1	_____			
RASH SYMPTOMS				
Skin Pain/Tenderness		Y	N	
Pruritus		Y	N	
Blistering/sloughing/epidermal detachment		Y	N	
If yes, please estimate total body surface area (TBSA) of blistered/detached skin _____%				
Pustules		Y	N	
Facial/ear edema		Y	N	
Other, Please specify _____				
Please estimate TBSA of all skin involvement _____%				
MUCOSAL INVOLVEMENT				
Ocular symptoms		Y	N	
Oral Symptoms		Y	N	
SYSTEMIC INVOLVEMENT				
Elevated AST, ALT, Alk Phos, and/or Tbili		Y	N	
Elevated total number of eosinophils: $\geq 500/\mu\text{L}$		Y	N	
$\geq 1500/\mu\text{L}$		Y	N	
HISTORY				
Please circle Y for yes, N for no, or UNK for Unknown				
Allergies to medicine		Y	N	UNK
Specify: _____				
Skin Problems		Y	N	UNK
Specify: _____				
TREATMENT FOR SKIN/MUCOSAL DISEASE				
High dose steroids $\geq 1$ mg/kg prednisone (or equivalent)		Y	N	
If yes, dated began: _____				
Low dose steroids $< 1$ mg/kg prednisone (or equivalent)		Y	N	
If yes, dated began: _____				
Topical steroids of any potency		Y	N	
Other, please specify _____				
Other, please specify _____				
PROCEDURE				
Did the subject undergo skin biopsy		Y	N	
Results: _____				
_____				
Did disease resolve in $\geq 15$ days?		Y	N	
Do you think this was a drug reaction?		Y	N	
If yes, what do you think is/are the likely culprit drug(s)? _____				
_____				

